9. SAFETY EVALUATION

9.1. Demographic and Other Baseline Characteristics

Demographic and other baseline characteristics will be summarized for all randomized subjects (ITT population). Ethnicity and race will be summarized by site (Table 92) and by randomized treatment group (Table 93). Ethnicity is categorized as Hispanic or Latino, or Not Hispanic or Latino. Race is categorized as American Indian or Alaska Native, Asian, Native Hawaiian or Other Pacific Islander, Black or African American, White, Multi-Racial, or Unknown. In accordance with NIH reporting policy, subjects may self-designate as belonging to more than one race (Multi-Racial) or may refuse to identify a race (Unknown), the latter reflected in the Case Report Form (CRF) as “No” to each racial option. Age will be summarized by site (Table 94) and by randomized treatment (Table 95).

Baseline sexual history will be summarized for all randomized subjects (ITT population). Categorical sexual history questions will be summarized by treatment group (Table 96) and continuous sexual history questions will be summarized by treatment group (Table 97).

Individual subject listings will be presented for all demographics, baseline and follow-up sexual history, and baseline pregnancy history (Listing 10, Listing 11, Listing 12, Listing 13, Listing 14, and Listing 15).

9.1.1. Prior and Concurrent Medical Conditions

All current illnesses and past pre-existing medical conditions will be MedDRA[®] coded using MedDRA dictionary version 20.1 or higher. Summaries of subjects' pre-existing and concurrent medical conditions will be presented by randomized treatment group for all sites and by each site in the ITT population (Table 98, Table 99, Table 100, Table 101, and Table 102).

Individual subject listings will be presented for all medical conditions (Listing 16).

9.1.2. Prior and Concomitant Medications

Summaries of medications that were started prior to dosing and continuing at the time of dosing as well as medications that were starting during dosing or during follow up will be presented by WHO Drug Anatomical codes (ATC) Level 1 and Level 2 and actual treatment group for subjects in the Safety population (Table 103, Table 104, Table 105, Table 106, and Table 107).

Individual subject listings will be presented for all concomitant medications (Listing 17).

9.2. Measurements of Treatment Compliance

All subjects are to receive a total of 25 doses of study product. The first dose is administered in clinic and the remaining doses will be administered by the subject at home. See Section 3.3.5 for the definition of compliance that will be used for analyses.

The number of subjects not compliant with study treatment will be presented by treatment group as part of the subject disposition table (Table 6). Treatment compliance is also a secondary outcome measure of the study; analyses and summaries are described in Section 8.2.

9.3. Adverse Events

When calculating the incidence of adverse events (i.e., on a per subject basis), each subject will only be counted once and any repetitions of adverse events within a subject will be ignored; the denominator will be the total safety population using the actual treatment group. All adverse events reported will be included in the

summaries and analyses. All analyses in Section 9.3 will be performed in the safety analysis population using the actual treatment received.

9.3.1. Solicited Events and Symptoms

Solicited local and systemic events will be captured on a memory aid starting on Day 1, the first day of therapy continuing through Visit 7 (Week 24, Day 168) and graded on a scale of 0 (absent), 1 (mild), 2 (moderate) and 3 (severe). Solicited local events include vaginal bleeding other than menstruation, abnormal vaginal discharge, abnormal vaginal odor, genital itching, genital burning, external genital irritation, external genital swelling, and genital rash. Solicited systemic events include nausea, vomiting, abdominal pain/cramps, diarrhea, constipation, pain/burning with urination, frequent urination, blood in urine, and headache.

Any symptom that is present at the time that the subject is screened or enrolled should be considered as baseline and not reported as a solicited AE. However, if it deteriorates at any time during the study, it will be recorded as a solicited AE. If a symptom is reported that was not present at baseline, it will also be recorded as a solicited AE. Treatment-emergent solicited adverse events will be identified by comparing the severity of the baseline solicited symptoms with the severity of the post-baseline solicited symptoms. If the severity increases post-baseline or the symptoms appear post-baseline when it was 'None' at baseline, then the symptom will be considered to be treatment-emergent.

The number and percent of subjects reporting at least one treatment-emergent solicited adverse event will be summarized for each solicited adverse event and any solicited adverse event along with the 95% Blaker CI and presented in [Table 108](#). Section 6.1 provides pseudo SAS code to use for calculating confidence intervals.

For each treatment-emergent solicited adverse event, the maximum severity over 24 weeks after the first dose will be summarized for the Safety population. The number and percentage of subjects reporting each solicited adverse event will be summarized by the maximum severity and actual treatment group along with the 95% Blaker CIs. For each event, the denominator is the number of subjects with non-missing data for the solicited adverse event being summarized. See [Table 109](#), [Table 110](#), [Table 111](#), and [Table 112](#) and [Figure 41](#) and [Figure 42](#).

The number of subjects reporting a solicited symptom will be summarized for each week for all subjects and separately for each treatment group ([Table 113](#), [Table 114](#), [Table 115](#), [Table 116](#), [Table 117](#), [Table 118](#), [Table 119](#), [Table 120](#), [Table 121](#), [Table 122](#), [Table 123](#), and [Table 124](#)) and graphically in a bar chart ([Figure 43](#) and [Figure 44](#)).

Solicited symptoms by subject will be presented in [Listing 18](#) and [Listing 19](#).

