11. Participants will be given a memory aid or a web link (with a username and temporary password) and instructed to make an entry following each insertion of a pre-filled applicator beginning with the first application at Visit 1 (Day 1). Any symptoms that occur during the study up until Visit 7 (Week 24, Day 168) will be recorded on the memory aid. Participants not using the web link will be reminded to return with the paper memory aid at each study visit where it will be reviewed.
12. Participants will be instructed to abstain from sexual intercourse during the first 5 days of study product administration, for 12 hours after the weekly study product applications and 12 hours before study Visit 2 (Week 4, Day 28), Visit 3 (Week 8, Day 56), Visit 4 (Week 12, Day 84) and Visit 7 (Week 24, Day 168).
13. Participants will receive non-spermicidal lubricated condoms for their male sexual partners who will be encouraged to use condoms from Visit 1 (Day 1) through Visit 7 (Week 24, Day 168) if they engage in vaginal intercourse.
14. Participants will be instructed not to use scented tampons or any other vaginal products through Visit 7 (Week 24, Day 168).
15. Participants will be advised to return for Visit 2 (Week 4, Day 28), Visit 3 (Week 8, Day 56) and Visit 4 (Week 12, Day 84) with allowable scheduling within 7 days of the target date. Depending on the time of the enrollment and the average length of the woman's menstrual cycle, careful attention should be paid to the approximate time of her next menstrual period when scheduling those visits. Later adjustments of those dates may be necessary.
16. Participants will be asked to collect all used applicators and store them as described in the MOP.
17. Participants will be asked to return all used applicators at their next visit.

Participants immediately diagnosed with yeast on the wet mount (with or without discharge or vaginitis symptoms) during the enrollment visit will be referred for standard treatment. They will not be randomized and will not be invited for rescreening.

If available test results at the enrollment visit suggest a UTI, cervicitis, vulvovaginitis, or active genital herpes lesion, the woman will be managed as clinically indicated and not randomized at this time, but invited for rescreening after completion of treatment.

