9.2 Methods and Timing for Assessing, Recording, and Analyzing Safety Parameters

9.2.1 Adverse Events

ICH (International Conference on Harmonisation) E6 defines an AE as any untoward medical occurrence in a patient or clinical investigation subject administered a pharmaceutical product regardless of its causal relationship to the study treatment. An AE can therefore be any unfavorable and unintended sign (including an abnormal laboratory finding), symptom, or disease temporally associated with the use of medicinal (investigational) product. The occurrence of an AE may come to the attention of study personnel during study visits and interviews of a study participant presenting for medical care, or upon review by a study monitor.

All AEs including local and systemic reactions not meeting the criteria for “serious adverse events” should be captured on the appropriate CRF and will include:

- Vaginal bleeding other than menstruation
- Abnormal vaginal discharge
- Abnormal vaginal odor
- Genital itching
- Genital burning
- External genital irritation
- External genital swelling
- Nausea
- Vomiting
- Abdominal pain/cramps
- Diarrhea
- Constipation
- Genital rash
- Pain/burning with urination
- Frequent urination
- Blood in urine
- Headache

Information to be collected includes event description, time of onset, clinician’s assessment of severity, relationship to study product (assessed only by those with the training and authority to make a diagnosis), and time of resolution/stabilization of the event. All AEs occurring while on study must be documented appropriately regardless of relationship. All AEs will be followed to adequate resolution.

Any medical condition that is present at the time that the participant is screened should be considered as baseline and not reported as an AE. However, if it deteriorates at any time during the study, it should be recorded as an AE. All AEs must be graded for severity and relationship to study product. The FDA defines an AE as any untoward medical occurrence associated with the use of a drug in humans, whether or not considered drug related. Severity of Event: All AEs will be assessed by the clinician using a protocol defined grading system. For events not included in the protocol defined grading system, then the following guidelines will be used to quantify intensity.

- Mild: Events require minimal or no treatment and do not interfere with the participant's daily activities.

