3.3.4. Baseline Value

The baseline value for most variables will be defined as the last value obtained prior to the first dose of LACTIN-V or placebo. As noted in Section 3.3.2, for BV recurrence, the baseline BV diagnosis will be the diagnosis at the screening visit.

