4.5. Efficacy and Safety Variables

For safety and efficacy analyses, multiple observations within specific visit period are accepted. In the case of multiple observations within a specific window, the assessment value that is closest to the scheduled visit window will be used in the analyses for the post-baseline records. The last observed value prior to administration of LACTIN-V or placebo will be used as the baseline value. All the recorded data will be listed. If observations have the same distance to the scheduled assessment, the latest one will be used.

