4.5.1. Safety Variables

Solicited local and systemic events are captured on a memory aid starting on Day 1, the first day of dosing daily through Week 1 and then weekly, continuing through Visit 7 (Week 24, Day 168). The subject is to record the presence and intensity of solicited events on the memory aid. Any event that is present at the time that the subject is screened should be considered as baseline and not reported as a solicited urogenital AE. However, if the symptom deteriorates at any time during the study, it is recorded as an AE. If a symptom is reported that is not present at baseline, it too is recorded as an AE. Solicited local events include vaginal bleeding other than menstruation, abnormal vaginal discharge, abnormal vaginal odor, genital itching, genital

burning, external genital irritation, external genital swelling, and genital rash. Solicited systemic events include nausea, vomiting, abdominal pain/cramps, diarrhea, constipation, pain/burning with urination, frequent urination, blood in urine, and headache.

Severity of solicited events symptoms are graded according to the tables in Appendix B and Appendix C in the protocol. Symptoms not specifically mentioned will be graded using the following scale:

- Mild: Events require minimal or no treatment and do not interfere with the subject's daily activities.
- Moderate: Events result in a low level of inconvenience or concern with the therapeutic measures. Moderate events may cause some interference with functioning.
- Severe: Events interrupt a subject's usual daily activity and may require systemic drug therapy or other treatment. Severe events are usually incapacitating.

Tolerability of LACTIN-V will be measured by identifying subjects who discontinue study product early due to adverse events.

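### The SAP gives conflicting baselines for treatment-emergent solicited symptoms; a screening baseline would leave out on-product discharge or odor no worse than before MetroGel

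*SAP*

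**What the plan says.** SAP 9.3.1 identifies treatment-emergent solicited events by comparing severity after baseline with severity at baseline: "If the severity increases post-baseline or the symptoms appear post-baseline" where there was none before, the event counts. The count therefore depends on the baseline, and the documents define it in three ways:

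- **Screening only.** SAP 4.5.1, on solicited events: "Any event that is present at the time that the subject is screened should be considered as baseline". Protocol 9.2.1 does the same for adverse events: "Any medical condition that is present at the time that the participant is screened should be considered as baseline".
- **Screening or enrollment.** SAP 9.3.1: "Any symptom that is present at the time that the subject is screened or enrolled should be considered as baseline". It gives no rule for when the two visits differ.
- **Last value before dosing.** SAP 3.3.4: "The baseline value for most variables will be defined as the last value obtained prior to the first dose of LACTIN-V or placebo"; the only exception it names is the BV diagnosis. SAP 4.5, in a paragraph that covers safety as well as efficacy analyses: "The last observed value prior to administration of LACTIN-V or placebo will be used as the baseline value".

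SAP 13, which lists changes from the protocol, does not mention the point. On grading, SAP 4.5.1 says: "Severity of solicited events symptoms are graded according to the tables in Appendix B and Appendix C in the protocol". In Appendix B, odor and vaginal discharge stop at Grade 2; the Grade 3 cell is marked not applicable.

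**The concern.** Screening falls 5 to 30 days before Day 1, when each woman has untreated BV. She then takes five days of MetroGel and is dosed at Visit 1. Her screening and pre-dose symptoms may therefore differ, and two programmers who each follow the SAP could produce different tables.

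The symptom most exposed is also the main expected local effect: protocol 2.3.1.1 lists vaginal discharge as the only most-likely adverse effect. The tested safety table, Table 125, covers product-related unsolicited events. Tables 108 to 110 are thus where cumulative treatment-emergent discharge and odor rates, with confidence intervals, would be read for Phase III planning.

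**Working it through.** The plan states no figure on this point, so there is none to reproduce. The check has two parts.

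**1. The rules applied to one woman.** Suppose discharge is Grade 1 at screening, absent at Visit 1 after MetroGel, and Grade 1 in Week 1 on product.

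- Screening baseline (SAP 4.5.1): 1 against 1, not counted.
- Last pre-dose baseline (SAP 3.3.4, 4.5): 1 against 0, counted.
- Screened or enrolled (SAP 9.3.1): undetermined; read literally, presence at screening is enough to make it baseline.

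If she was Grade 2 at screening, the screening rule can never count her for that symptom in 24 weeks, because Appendix B has nothing above Grade 2. (SAP 9.3.1 and the table shells also list a severe level, but SAP 4.5.1 sends grading to Appendix B.) The plus sign for treatment-emergent events in Listing 18 depends on the same choice.

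**2. Illustrative size.** Inputs:

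- Arms: 228 × 2/3 = 152 LACTIN-V and 228 × 1/3 = 76 placebo (SAP 5).
- r, the share of an arm with product-caused discharge: 46%, borrowed from the Phase II-a figure in protocol 2.3.1.1 (24 women, arms combined). Protocol 2.1 says less powder is now needed, so 20% is also tried. Both values are assumptions for this trial.
- s, the share of those women who had discharge at screening that cleared by Visit 1: assumed 0 to 75%.
- w, the share of the s group whose on-product grade exceeds the screening grade: assumed 0 or 25%.

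Rate counted under a screening baseline = r × [1 − s(1 − w)]. With r = 46%, 0.46 × 152 = 69.9, or about 70 LACTIN-V women:

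| s | w = 0 | w = 25% |
|---|---|---|
| 0% | 46% (70 women) | 46% (70) |
| 25% | 34.5% (52) | 37% (57) |
| 50% | 23% (35) | 29% (44) |
| 75% | 11.5% (17) | 20% (31) |

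The points left out are r × s × (1 − w). With w = 0 and s = 25% to 75%, that is 5 to 15 points at r = 20% and 11.5 to 34.5 points at r = 46%.

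For scale, the 95% half-width of one arm's rate, 1.96 × √[r(1 − r)/n], is 6.4 points (r = 20%) to 7.9 points (r = 46%) with 152 women, and 9.0 to 11.2 points with 76.

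If s and w are alike in the two arms, as randomization should make them on average, a true difference shrinks by the same factor. For example, with w = 25%, a true 46% against 26% (20 points) shows as 20 × 0.8125 = 16.3, 20 × 0.625 = 12.5 or 20 × 0.4375 = 8.8 points at s = 25%, 50% or 75%.

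**The case against.** The strongest reply is that SAP 4.5 already governs the comparison, and that the screening sentences only say what to record as an adverse event. On that reading the tables already use the pre-dose value, and the defect is loose wording. The reading is possible, but the SAP does not state it. Sections 4.5.1 and 9.3.1 are the specific provisions for solicited events, and as written they point to screening.

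Three other replies stand in full:

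- **An Amsel sign is not a graded symptom.** A reader might infer that, since three of four Amsel criteria require the discharge sign or a positive whiff test, every woman started with discharge or odor. The documents do not support this. The first is a clinician's finding and the second a bench test. In Appendix B, a woman who reports her usual amount of discharge and no odor complaint is Grade 0 on both. Asymptomatic BV is eligible, so s may be near zero.
- **Much of the information appears elsewhere.** Weekly Tables 113 to 118 are not described as limited to treatment-emergent symptoms, and Tables 115 to 118 are by arm. Tables 133 to 135 give clinician-observed abnormal discharge at Visits 1 to 4. None of these gives a cumulative treatment-emergent proportion with an interval.
- **A pre-dose baseline has its own weakness.** Protocol 7.2 and SAP 3.3.2 accept that BV may still be resolving at Visit 1. The memory aid starts only with dosing; women are "instructed to make an entry following each insertion of a pre-filled applicator beginning with the first application at Visit 1". The schedule of events starts symptom review at Visit 2. No form is named for pre-dose severity.

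**Conclusion.** The conflict is real and worth correcting; its numerical effect is not established. If the screening rule is applied, product-related discharge and odor in Tables 108 to 110 are under-counted in both arms and the difference between arms shrinks. The loss runs from zero to the assumed upper values above, and the documents give neither s nor w. For the systemic symptoms in Tables 111 and 112 only the conflict of definitions applies. Tables 108 to 112 carry no hypothesis test, and Table 125 is unaffected.

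A reader might go further in two ways. One is to infer a bias in favor of LACTIN-V; the documents do not support this, because screening symptoms precede randomization and should balance. The other is to infer that pooling over 24 weeks hides a product excess behind BV recurrence symptoms, so that a separate early-window table is required. That is a preference. Take the planning recurrence rates of 30% and 15%, and assume other discharge in 20% of women and a countable symptom in half of recurrences. With no product excess at all, placebo exceeds LACTIN-V by 0.8 × 0.5 × (0.30 − 0.15) = 6.0 points. An all-cause table should show that, since it reflects fewer recurrences.

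**What to change.** In SAP 4.5.1 and 9.3.1, replace the screening wording with the SAP's own general rule:

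> *Baseline for each solicited symptom is the last severity recorded before the first dose of study product, taken from [named form]. If no severity was recorded at Visit 1, the screening severity is used, and the number of such subjects is shown by treatment group.*

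List this in SAP 13 as a change from protocol 9.2.1, and settle it before unblinding. A Day 1 to Visit 2 table may be added but is optional.

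The cost is wording and minor programming. The change depends on what was graded before dosing. Where Visit 1 severity is missing, the fallback brings back the screening baseline, which is why the counts by arm are needed. A pre-dose baseline also lets somewhat more recurrence symptoms count over 24 weeks. On the planning rates, and with other discharge in 20%, raising the countable share of recurrences from an assumed 10% to 50% moves their contribution to the difference between arms from 0.8 × 0.1 × 0.15 = 1.2 points to 6.0 points.

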4.4. Treatments

4.4.1. Treatments Administered

Each subject will receive one box of MetroGel vaginal gel sufficient for the 5-day course of treatment.

Women will return to the study clinic within 2 days after completing the 5-day course of MetroGel to re-evaluate eligibility criteria and review the BV test results from the screening visit. Women with Amsel criteria ≥ 3 and Nugent score 4-10 will be randomized.

Subjects will administer the first dose of LACTIN-V or Placebo under direct supervision by the study clinician before leaving the clinic (Day 1). Subjects will be instructed to administer one dose once a day at bedtime for the next 4 days (beginning on Day 2), and then two times a week for 10 weeks. The remaining 20 applicators will be used for the two doses each week during weeks 2 through 11.

The dates of first treatment are presented for subjects in the Safety population by site in [Table 3](#) and actual treatment group in [Table 4](#).

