Vaginal bleeding other than menstruation	None	x	x	x	x	x	x	x	x	x	x	x	x	x	x
	Mild	x	x	x	x	x	x	x	x	x	x	x	x	x	x
	Moderate	x	x	x	x	x	x	x	x	x	x	x	x	x	x
	Severe	x	x	x	x	x	x	x	x	x	x	x	x	x	x
Abnormal vaginal discharge	None	x	x	x	x	x	x	x	x	x	x	x	x	x	x
	Mild	x	x	x	x	x	x	x	x	x	x	x	x	x	x
	Moderate	x	x	x	x	x	x	x	x	x	x	x	x	x	x
	Severe	x	x	x	x	x	x	x	x	x	x	x	x	x	x
Abnormal vaginal odor	None	x	x	x	x	x	x	x	x	x	x	x	x	x	x
	Mild	x	x	x	x	x	x	x	x	x	x	x	x	x	x
	Moderate	x	x	x	x	x	x	x	x	x	x	x	x	x	x
	Severe	x	x	x	x	x	x	x	x	x	x	x	x	x	x
Genital itching	None	x	x	x	x	x	x	x	x	x	x	x	x	x	x
	Mild	x	x	x	x	x	x	x	x	x	x	x	x	x	x
	Moderate	x	x	x	x	x	x	x	x	x	x	x	x	x	x
	Severe	x	x	x	x	x	x	x	x	x	x	x	x	x	x

Treatment Group=All (N=X)															
		Week 7 (N=X)		Week 8 (N=X)		Week 9 (N=X)		Week 10 (N=X)		Week 11 (N=X)		Weeks 12-18 (N=X)		Weeks 19-24 (N=X)	
Solicited Adverse Event	Severity ¹	n	%	n	%	n	%	n	%	n	%	n	%	n	%
	Genital burning	None	x	x	x	x	x	x	x	x	x	x	x	x	x
Mild		x	x	x	x	x	x	x	x	x	x	x	x	x	x
Moderate		x	x	x	x	x	x	x	x	x	x	x	x	x	x
Severe		x	x	x	x	x	x	x	x	x	x	x	x	x	x
External genital irritation	None	x	x	x	x	x	x	x	x	x	x	x	x	x	x
	Mild	x	x	x	x	x	x	x	x	x	x	x	x	x	x
	Moderate	x	x	x	x	x	x	x	x	x	x	x	x	x	x
	Severe	x	x	x	x	x	x	x	x	x	x	x	x	x	x
External genital swelling	None	x	x	x	x	x	x	x	x	x	x	x	x	x	x
	Mild	x	x	x	x	x	x	x	x	x	x	x	x	x	x
	Moderate	x	x	x	x	x	x	x	x	x	x	x	x	x	x
	Severe	x	x	x	x	x	x	x	x	x	x	x	x	x	x
Genital rash	None	x	x	x	x	x	x	x	x	x	x	x	x	x	x
	Mild	x	x	x	x	x	x	x	x	x	x	x	x	x	x
	Moderate	x	x	x	x	x	x	x	x	x	x	x	x	x	x
	Severe	x	x	x	x	x	x	x	x	x	x	x	x	x	x

Notes: Denominator for percentages is the number of subjects in the Safety Population (N) completing memory aid that week.
¹The maximum severity of any solicited adverse event is summarized. A subject is only counted once at the maximum severity.

Tables with Similar Format:

Table 115: Number and Percentage of Subjects Experiencing Solicited Local Events by Symptom, Severity, Week, and Treatment Group—Safety Population—LACTIN-V—Weeks 1-6

Table 116: Number and Percentage of Subjects Experiencing Solicited Local Events by Symptom, Severity, Week, and Treatment Group—Safety Population—LACTIN-V—Weeks 7-24

Table 117: Number and Percentage of Subjects Experiencing Solicited Local Events by Symptom, Severity, Week, and Treatment Group—Safety Population—Placebo—Weeks 1-6

Table 118: Number and Percentage of Subjects Experiencing Solicited Local Events by Symptom, Severity, Week, and Treatment Group—Safety Population—Placebo—Weeks 7-24

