Solicited Adverse Event	Severity ¹	Week 7 (N=X)		Week 8 (N=X)		Week 9 (N=X)		Week 10 (N=X)		Week 11 (N=X)		Weeks 12-18 (N=X)		Weeks 19-24 (N=X)	
		n	%	n	%	n	%	n	%	n	%	n	%	n	%
Any Solicited Systemic Event	None	x	x	x	x	x	x	x	x	x	x	x	x	x	x
	Mild	x	x	x	x	x	x	x	x	x	x	x	x	x	x
	Moderate	x	x	x	x	x	x	x	x	x	x	x	x	x	x
	Severe	x	x	x	x	x	x	x	x	x	x	x	x	x	x
Nausea*	None	x	x	x	x	x	x	x	x	x	x	-	-	-	-
	Mild	x	x	x	x	x	x	x	x	x	x	-	-	-	-
	Moderate	x	x	x	x	x	x	x	x	x	x	-	-	-	-
	Severe	x	x	x	x	x	x	x	x	x	x	-	-	-	-
Vomiting*	None	x	x	x	x	x	x	x	x	x	x	-	-	-	-
	Mild	x	x	x	x	x	x	x	x	x	x	-	-	-	-
	Moderate	x	x	x	x	x	x	x	x	x	x	-	-	-	-
	Severe	x	x	x	x	x	x	x	x	x	x	-	-	-	-
Abdominal pain/cramps*	None	x	x	x	x	x	x	x	x	x	x	-	-	-	-
	Mild	x	x	x	x	x	x	x	x	x	x	-	-	-	-
	Moderate	x	x	x	x	x	x	x	x	x	x	-	-	-	-
	Severe	x	x	x	x	x	x	x	x	x	x	-	-	-	-
Diarrhea*	None	x	x	x	x	x	x	x	x	x	x	-	-	-	-
	Mild	x	x	x	x	x	x	x	x	x	x	-	-	-	-
	Moderate	x	x	x	x	x	x	x	x	x	x	-	-	-	-
	Severe	x	x	x	x	x	x	x	x	x	x	-	-	-	-

Treatment Group=All (N=X)															
		Week 7 (N=X)		Week 8 (N=X)		Week 9 (N=X)		Week 10 (N=X)		Week 11 (N=X)		Weeks 12-18 (N=X)		Weeks 19-24 (N=X)	
Solicited Adverse Event	Severity ¹	n	%	n	%	n	%	n	%	n	%	n	%	n	%
Constipation*	None	x	x	x	x	x	x	x	x	x	x	-	-	-	-
	Mild	x	x	x	x	x	x	x	x	x	x	-	-	-	-
	Moderate	x	x	x	x	x	x	x	x	x	x	-	-	-	-
	Severe	x	x	x	x	x	x	x	x	x	x	-	-	-	-
Pain/burning with urination	None	x	x	x	x	x	x	x	x	x	x	x	x	x	x
	Mild	x	x	x	x	x	x	x	x	x	x	x	x	x	x
	Moderate	x	x	x	x	x	x	x	x	x	x	x	x	x	x
	Severe	x	x	x	x	x	x	x	x	x	x	x	x	x	x
Frequent urination	None	x	x	x	x	x	x	x	x	x	x	x	x	x	x
	Mild	x	x	x	x	x	x	x	x	x	x	x	x	x	x
	Moderate	x	x	x	x	x	x	x	x	x	x	x	x	x	x
	Severe	x	x	x	x	x	x	x	x	x	x	x	x	x	x
Blood in urine*	None	x	x	x	x	x	x	x	x	x	x	-	-	-	-
	Mild	x	x	x	x	x	x	x	x	x	x	-	-	-	-
	Moderate	x	x	x	x	x	x	x	x	x	x	-	-	-	-
	Severe	x	x	x	x	x	x	x	x	x	x	-	-	-	-
Headache*	None	x	x	x	x	x	x	x	x	x	x	-	-	-	-
	Mild	x	x	x	x	x	x	x	x	x	x	-	-	-	-
	Moderate	x	x	x	x	x	x	x	x	x	x	-	-	-	-
	Severe	x	x	x	x	x	x	x	x	x	x	-	-	-	-

Notes: Denominator for percentages is the number of subjects in the Safety Population (N) completing memory aid that week.
 *Symptom not collected during weeks 12-24.
¹The maximum severity of any solicited adverse event is summarized. A subject is only counted once at the maximum severity.

Tables with Similar Format:

Table 121: Number and Percentage of Subjects Experiencing Solicited Local Events by Symptom, Severity, Week, and Treatment Group—Safety Population—LACTIN-V—Weeks 1-6

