Figure 41: Maximum Severity of Solicited Local Adverse Events by Symptom and Treatment Group - Safety Population	142
Figure 42: Maximum Severity of Solicited Systemic Adverse Events by Symptom and Treatment Group - Safety Population	143
Figure 43: Maximum Severity of Solicited Local Adverse Events by Day and Treatment Group—Safety Population	144
Figure 44: Maximum Severity of Solicited Systemic Adverse Events by Day and Treatment Group—Safety Population	144
Figure 45: Frequency of Adverse Events by MedDRA System Organ Class and Severity	145
Figure 46: Incidence of Adverse Events by MedDRA System Organ Class and Maximum Severity	146
Figure 47: Frequency of Adverse Events by MedDRA System Organ Class and Relationship to Treatment.....	147
Figure 48: Incidence of Adverse Events by MedDRA System Organ Class and Relationship to Treatment.....	148

Figure 1: CONSORT Flow Diagram

Implementation notes: The actual diagram will match the design of this study.

[figure not shown]

Figure 2: Time to BV Recurrence by Visit 4 (Week 12) by Treatment Group

[figure not shown]

Figure will be a 2x2 panel plot with each panel displaying one of the analysis populations: ITT, mITT, CC, and PP.

[figure not shown]
Figures with similar format:

Figure 3: Time to BV Recurrence by Visit 7 (Week 24) by Treatment Group

Figure 4: Time to *L. crispatus* Colonization by Visit 4 (Week 12) by Treatment Group

Figure 5: Time to *L. crispatus* Colonization by Visit 7 (Week 24) by Treatment Group

[figure not shown]
Figure 6: *L. crispatus* CTV-05 Concentration by Time Since Last Dose, Week, and Treatment Group-ITT Population

Figures with similar format:

- Figure 7:** *L. crispatus* CTV-05 Concentration by Time Since Last Dose, Week, and Treatment Group-mITT Population
- Figure 8:** *L. crispatus* CTV-05 Concentration by Time Since Last Dose, Week, and Treatment Group-CC Population
- Figure 9:** *L. crispatus* CTV-05 Concentration by Time Since Last Dose, Week, and Treatment Group-PP Population
- Figure 10:** *L. crispatus* CTV-05 Concentration by Number of Condom-less Sexual Intercourse Acts, Week, and Treatment Group-ITT Population
- Figure 11:** *L. crispatus* CTV-05 Concentration by Number of Condom-less Sexual Intercourse Acts, Week, and Treatment Group-mITT Population
- Figure 12:** *L. crispatus* CTV-05 Concentration by Number of Condom-less Sexual Intercourse Acts, Week, and Treatment Group-CC Population

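### The weekly solicited-symptom tables switch from one-week columns to 7- and 6-week maximum-severity columns where scheduled dosing ends, so percentages before and after Week 11 are not on the same scale

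*SAP*

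**What the plan says.** - **Unit of the summary.** SAP 9.3.1 commits to weekly summaries: "The number of subjects reporting a solicited symptom will be summarized for each week for all subjects and separately for each treatment group". It cites Tables 113-124, then Figures 43 and 44 as bar charts.
- **Collection.** SAP 4.5.1 describes memory-aid capture from "the first day of dosing daily through Week 1 and then weekly, continuing through Visit 7 (Week 24, Day 168".
- **Dosing schedule.** After the five daily doses of Week 1, SAP 4.4.1 says: "The remaining 20 applicators will be used for the two doses each week during weeks 2 through 11". Scheduled dosing therefore covers Weeks 1-11.
- **Shells.** In SAP Appendix 1, Table 113 has single columns for Weeks 1-6. Table 114 has single columns for Weeks 7-11, then two columns headed Weeks 12-18 and Weeks 19-24. Table 120 has the same columns for systemic symptoms. Tables 116 and 118 follow Table 114. Tables 122 and 124 are listed under Table 120 as having its format, although their titles say local.
- **Counting rule.** The footnotes count each subject once, at maximum severity.
- **Denominator.** "Denominator for percentages is the number of subjects in the Safety Population (N) completing memory aid that week".
- **Systemic symptoms after Week 11.** Seven of the nine carry the note "Symptom not collected during weeks 12-24". Only pain/burning with urination and frequent urination have entries there.

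SAP section 13, which lists changes to the planned analyses, does not mention the pooling.

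**The concern.** A one-week column estimates the percentage of women with a symptom in that week. A seven-week column scored by maximum severity estimates the percentage with the symptom in at least one of seven weeks. These are different quantities, and they sit side by side in one row. The change of scale falls between Week 11 and Week 12, where scheduled dosing ends. A reader going along the row to see whether a symptom settles after the last dose meets a built-in step upwards.

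Protocol 2.3.1.1 names vaginal discharge as the most likely effect of the product, so its course after dosing is of real interest. Tables 108-112 reduce the 24 weeks to ever/never or to one maximum and cannot show it. Tables 113-124 are the planned tables laid out by week.

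The denominator is a second gap. For a pooled column, completing the memory aid in that week could mean at least one of the seven weeks, all seven, or something between. The programmer would have to choose.

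**Working it through.** The plan states no computed figure on this point, so there is none to reproduce.

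**Column widths, from the shells.** Weeks 1-11 are 11 single columns. Weeks 12-18 are 7 weeks and Weeks 19-24 are 6. 11 + 7 + 6 = 24. Doses are 5 + 2 × 10 = 25, ending in Week 11.

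**Assumptions.** The documents give neither weekly symptom rates nor the correlation between weeks in the same woman. Let q be the weekly rate and ρ that correlation, and assume every week is completed.

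**Formula.** A column of m weeks prints the probability of at least one report:

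- ρ = 0: 1 − (1 − q)^m
- 0 < ρ < 1 (beta-binomial): 1 − ∏ (b + i)/(a + b + i) for i = 0 to m − 1, with a = q(1/ρ − 1) and b = (1 − q)(1/ρ − 1)
- ρ = 1: q

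Example: q = 0.05, m = 7, ρ = 0 gives 1 − 0.95^7 = 0.302.

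**What the pooled columns print**

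| Weekly rate | Column | ρ = 0 | 0.2 | 0.5 | 0.8 | 1 |
|---|---|---|---|---|---|---|
| 5% | 7 weeks | 30.2% | 20.0% | 12.3% | 7.5% | 5% |
| 5% | 6 weeks | 26.5% | 18.4% | 11.7% | 7.3% | 5% |
| 10% | 7 weeks | 52.2% | 36.5% | 23.5% | 14.7% | 10% |
| 10% | 6 weeks | 46.9% | 33.9% | 22.3% | 14.4% | 10% |

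**A true halving from 20% to 10% per week.** On one scale it prints as 20% then 10%. In about 152 LACTIN-V women (2/3 of 228) that is about 30 women, then 15. The 7-week column would instead show about 79 women (52.2%) at ρ = 0, 55 (36.5%) at 0.2 and 36 (23.5%) at 0.5. All three read as a rise. At ρ = 0.8 it prints 14.7%, a fall but an understated one.

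**Break-even.** Starting from 20% per week, the later weekly rate that makes the 7-week column also print 20% is:

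| ρ | Later weekly rate | True fall that prints as flat |
|---|---|---|
| 0 | 3.1% | 84% |
| 0.2 | 5.0% | 75% |
| 0.5 | 8.4% | 58% |
| 0.8 | 13.8% | 31% |

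A smaller true fall prints as a rise. A larger one prints as a fall that is too small.

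**A fall from 15% to 5% per week.** Week 11 prints 15%. From the 5% row above, Weeks 12-18 prints 30.2%, 20.0%, 12.3% or 7.5% at ρ = 0, 0.2, 0.5 or 0.8. It reads as a rise only if ρ is below about 0.37.

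**Severity moves too.** Take a weekly mild/moderate/severe split of 7.5/2/0.5% and seven independent weeks:

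- No symptom: 0.900^7 = 0.478
- At most mild: 0.975^7 = 0.838
- At most moderate: 0.995^7 = 0.966

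The column prints about 36% mild, 13% moderate and 3% severe. A week with double the underlying rates prints 15/4/1%.

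**The any-systemic row.** It draws on 9 symptoms to Week 11 and on 2 afterwards. That pushes the row down while pooling pushes it up, so it is not comparable across Week 11 for two reasons.

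**The case against.** The strongest case against is that these are descriptive tables with plainly labelled columns. No objective or hypothesis compares symptoms before and after dosing within an arm. In a placebo-controlled trial the product effect is judged between arms, and both arms share the column widths. That stands, and it limits the point to the reading over time.

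Several stronger readings are tempting, and the documents do not support them:

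- **That resolution after dosing is always hidden or reversed.** The direction depends on rates and correlations the documents do not give. In the 15% to 5% example, a correlation of 0.5 or more still prints as a fall. Only the inflation is general, and it vanishes if symptoms are fully persistent.
- **That no other planned output shows the time course.** The sentence in 9.3.1 goes on to Figures 43 and 44, the first titled "Maximum Severity of Solicited Local Adverse Events by Day and Treatment Group". The images are not available, so whether they separate Weeks 12-24 cannot be told. Listings 18 and 19 carry week and study day. Tables 133-135 describe discharge at examination by visit, but stop at Visit 4.
- **That the pooled columns are exactly the off-product period.** They follow the schedule, not exposure. SAP 4.4.3 can be read as allowing make-up doses after Week 11, Protocol 7.5 describes dosing resuming after retreatment at Visit 4, and some women stop early.
- **That all systemic symptoms are affected.** Seven of nine have no entry after Week 11.

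One uncertainty remains. The memory-aid form is not in the documents, and the systemic footnote shows that collection after Week 11 differs from the general description in 4.5.1. If Weeks 12-24 were recorded by period, the shells are right and the text is wrong. The two conflict either way.

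**Conclusion.** The point holds as a fault in the layout of the weekly solicited-symptom tables. The text promises weekly summaries. The shells give weekly figures for scheduled dosing and multi-week maxima afterwards, with a denominator that does not fit the pooled columns. The later percentages are inflated relative to the weekly ones unless symptoms are fully persistent. Over the assumed range of ρ from 0 to 0.5, a 5% weekly rate prints as 30.2% to 12.3% in the 7-week column and a 10% rate as 52.2% to 23.5%. A real fall after dosing can therefore appear smaller than it is, flat or reversed. Which of these occurs cannot be settled from the documents.

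The fault covers the eight local symptoms, the any-local row, two systemic symptoms and, with the added change of components, the any-systemic row. A reader might infer that the safety conclusions are compromised. They are not: comparison of arms within a column, Tables 108-112 and the primary safety test in Table 125 are untouched. The change should be made, but nothing inferential depends on it.

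**What to change.** 1. In Tables 114, 116 and 118, give Weeks 12-24 one column per week, as 9.3.1 says. Alternatively, print the average weekly percentage (memory-aid weeks with the symptom divided by memory-aid weeks completed) for Weeks 1-11, 12-18 and 19-24, so that all periods share one scale and one defined denominator.
2. In Tables 120, 122 and 124, do the same only for pain/burning with urination and frequent urination. Add a footnote that the any-systemic row drops from nine component symptoms to two after Week 11.
3. If Weeks 12-24 were in fact collected by period, correct 4.5.1 and 9.3.1 instead. Define the denominator for the pooled columns and label them as not comparable with the weekly ones.

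The cost is a shell edit and a few extra columns. If collection was weekly as 4.5.1 states, no new data are needed. No test changes.
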